Unique Protocol ID: JCHP-2

Brief Title: Omega-3 Supplementation to Both Parent and Adolescent

Official Title: Omega-3 Supplementation to Both Parent and Adolescent to Reduce Behavior Problems

Document Date: May 16, 2018

Experimental Design and Methods

This section provides the design and method of the overarching study within which the three aims will be tested. We also briefly specify further programmatic goals of this line of study, and also how the specific expertise of the research team will help ensure feasibility. As with the pilot study, methodology and ultimately reporting of results will follow CONSORT 2010 guidelines (Moher et al., 2010).

Design Overview

The study design will consist of a stratified, double-blind, placebo-controlled, factorial, randomized controlled trial of children and their caregivers in a community sample in Mauritius. This closely follows the design of the pilot study (Raine et al. 2015). Unlike the pilot study however, it will utilize a 2x2 factorial design, in which children *and* their parents will be randomly assigned to either omega-3 supplementation (treatment condition) or a placebo (control condition), and will have an extended follow-up at 18 months. This results in 4 groups: (1) child and caregiver both receiving omega-3, (2) child receives omega-3, caregiver receives placebo, (3) caregiver receives omega-3, child receives placebo, (4) both parent and child receive placebo. Assessments will take place at 0 months (baseline), 6 months (end of supplementation), 12 months (6 months post-treatment), and 18 months (12 months post-treatment).

Background To The Sample and the Mauritius Child Health Project

Adolescents and caregivers will be drawn from the Mauritius Child Health Study, a multi-generational study involving three generations of subjects. Details of these three generations are provided in a cohort profile (Raine et al. 2010). Originally set up by [name] (Consultant), this longitudinal study covers early child health and development and the identification of early risk factors (including nutrition) for later psychopathology, as well as early primary prevention. Early factors that shape later cognitive functioning have also been a focus. Given the pilot findings and longitudinal data on the parents, it provides a unique platform on which to build.

Participants, Potential Attrition, and Strategies to Deal with Attrition

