Participants will consist of 400 pairs of children and their caregivers (total N = 800). This replicates cell sizes in the pilot data and allows close comparability, with 100 children and 100 adults in each of four cells. The caregivers consist of the second generation participants (their parents are the first generation) who originally comprised the birth cohort. Their adolescent children are the third generation. All caregivers have previously participated in the Mauritius Child Health Project (Raine et al., 2010). Adolescents will be aged between 11 and 18 years old, willing to participate in an RCT, and residing in the community. Exclusion criteria consist of: (1) allergy to fish or fish products, (2) use of fish oil supplementation in the past six months, (3) intellectual disability, (4) participation in the prior RCT. There are currently 1,126 children aged 11-18 years actively participating in the Mauritius Child Health Project (51.2% female; 73.2% Indian, 24.5% Creole, 2.3% other), 124 of whom took part in the prior RCT and will be excluded. Written informed consent will be obtained from the parents with assent obtained from adolescents. The study will take place in interview rooms at the project headquarters in Quatre Bornes.

Attrition is an issue in all RCTs. In our pilot data however, attrition was only 8%, even after one year, and is likely attributable both to the long-standing intergenerational relationships between our research team in Mauritius and the participants. Attrition may nevertheless be slightly more with the longer follow-up. We have three strategies to deal with attrition. First, analyses will be intention-to-treat, including all participants regardless of drop-outs. Second, we will enhance participation using staggered incentives for completion. Third, we will code for missingness and assess whether it moderates treatment outcome.

Randomization

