Participants will be randomized into four groups using urn randomization, a covariate adaptive randomization method (Wei & Lachin, 1988). Adaptive randomization is employed because it protects the study from bias while promoting study objectives, it improves power over standard designs, and it balances assignment of treatment across covariates in a way superior to traditional stratification (Rosenberger et al., 2012). We aim to achieve balanced groups on three main child covariates: age, gender, and ethnicity. An advantage of the Mauritius cohort is that we have data on the parents' externalizing behavior over the life-course (Raine et al. 2010) which we could add as a fourth covariate to further ensure that groups are balanced.

Omega-3 Intervention

Omega-3 supplementation. As in the pilot study, this consists of a 200 ml drink. The base drink in both treatment and placebo conditions consists of fruit juice containing vitamin D (0.85 micrograms) and antioxidants (ferric reducing ability of plasma value of 0.71 mmol/100g). For the treatment condition only, 1660 mg of omega-3 (550 mg of DHA, 550 mg of EPA, 560 mg of alpha-linolenic acid) is added to the base drink. Placebo drinks are matched exactly with the fish-oil drink in terms of size, appearance, and flavor. Caregiver and child drinks are differentially color-coded.

This drink is chosen because: (i) it contains a higher dosage of omega-3 than standard capsules in a small liquid quantity (60.6% of a standard can of cola) suitable for child / adolescent consumption, (ii) the fruit-flavored drink may be better tolerated and result in higher compliance with children than fish-oil capsules.

Treatment duration and administration. As in the pilot study, treatment duration will be six months. It was chosen because prior studies have usually been 2 - 4 months (Sinn et al., 2010), and a longer duration may be more effective in producing longer-term behavioral change. The drink will be administered by the parents to their children at any time each day.

Primary Outcome Measures

The pre-defined primary outcome measures are externalizing behavior problems. Secondary outcomes included internalizing behavior problems and neurocognitive / academic mediators. We include additional *secondary* measures of reactive-proactive aggressive behavior and callous-unemotional traits to replicate the pilot findings and explore antisocial subtypes (the pilot data showed stronger effects for reactive aggression).

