Externalizing and internalizing behavior problems in children and caregivers will be assessed using the Multicultural Family Assessment Module (MFAM - Achenbach et al., 2015) which constitutes counterpart scales of the Child Behavior Checklist (CBCL/6-18), Youth Self-Report (YSR), Adult Self-Report (ASR), and Adult Behavior Checklist (ABCL). Reliability, validity, and cross-cultural generalizability have been documented in over 100 societies (Achenbach & Rescorla, 2001; Achenbach & Rescorla, 2001; Rescorla et al., 2012). The Externalizing scale includes Aggressive Behavior and Rule-Breaking Behavior, while the Internalizing scale includes Anxious/Depressed, Withdrawn, and Somatic Complaints. Additional syndromes include Attention Problems, Social Problems, and Thought Problems. Instruments are also scored on DSM-oriented scales comprising items judged by international clinical experts to be very consistent with DSM diagnostic criteria.

Adolescents will rate themselves on the Youth Self-Report YSR. The caregiver will rate their child on the CBCL/6-18, themselves on the ASR, and their spouse on the ABCL. We have established measurement invariance of the CBCL in this cohort in Mauritius (Yarnell et al., 2013). Teacher ratings of the child will be assessed using the Teacher Report Form of the MFAM. In consultation with [name] (Consultant), we will adopt the same system he has used in his national surveys to successfully obtain individual-based teacher ratings using payment to the teacher with a parental permission letter (Achenbach & Rescorla, 2001).

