The parent (CBCL) and youth (YSR) reports also include School Competence scales, while the teacher (TRF) form includes Academic Performance and Adaptive Functioning (Achenbach et al., 2015). These will extend the scope on mechanistic processes beyond neurocognitive functioning.

As in the pilot study, parental belief in treatment allocation to the omega-3 group (yes, no) will be measured at the end of treatment to assess influence on behavioral change. Demographics will again be collected on entry into the study, together with an adverse events questionnaire at the end of treatment.

Adherence to protocol and blood assays.

Adherence to the treatment regimen is a frequent problem in RCTs. As before, this will be assessed by assays of omega-3 from finger-prick blood taken from both caregiver and adolescent at all four time-points, with microwave irradiation assays conducted by team member [name] an NIAAA. For full methodological details see Lin, Loewke, Hyun, Leazer, & Hibbeln (2012). In response to C2, blood will additionally be assessed mid-way through supplementation (3 months). To help further enhance adherence, participants will be called every two weeks to remind them to use supplements, and to assess frequency of drink consumption by caregiver and adolescent in that time period (number of drinks / two weeks). To further facilitate compliance, participants will be given a bonus payment if their % blood omega-3 levels have risen higher than the bottom quartile of the population.

Statistical Methods

Overview. An intention-to-treat (ITT) design using all randomly assigned participants will be employed for all data analyses. All data will be blindly double-entered and checked for consistency.

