Aims 1 and 2 (Primary Outcome). These hypotheses will be addressed using adolescent and caregiver externalizing responses gathered at baseline and at 6, 12, and 18 month follow-ups. Responses for the adolescent will be analyzed separately from responses for the caregiver. For each separate set of responses, linear mixed effects models (Molenberghs & Verbeke, 2005) will be used to describe both the pattern of response and the within-subject covariance structure across time points. Primary analyses will not include baseline covariates, as the randomization will balance the treatment groups and eliminate selection bias. To enhance power by controlling for variability in response (Kahan et al., 2014), a small set of baseline covariates (e.g. gender, age, ethnicity) will be included in supplementary analyses.

The response may be transformed (e.g. log transformation) to reduce levels of skewness in the response to acceptable levels, as assessed by examination of residuals. Models will include binary indicators for adolescent group (omega-3 vs placebo), caregiver group (omega-3 vs placebo), and time (four level factor for times 0, 6, 12, and 18), and group by time interaction terms, as fixed effects. Time is modeled as a discrete factor to accommodate the patterns observed in our prior study (see Figure under Preliminary Data) where the omega-3 adolescent groups are similar at baseline and 6 months, and separate at 12 months. Covariance structure models (e.g. random effects, autocorrelated residuals) will be compared using information criteria in models containing all main effects and interactions of interest. Once the covariance structure has been chosen, the fixed effects will be assessed for significance using likelihood ratio tests.

Parameter estimates, standard errors, and 95% confidence intervals will be reported. In the case of a multiple degree of freedom test (e.g. group by time interaction, with 3 df), single-df contrasts will be estimated and reported, to explain the nature of the interaction.

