For the adolescent, Hypothesis 1a will be addressed using a child group by time interaction term (time trends for omega-3 and placebo group need not be parallel), or a child group main effect if the interaction term is non-significant (parallel time trends). Similar models will address the corresponding Hypothesis 1b for the caregiver responses. For both the adolescent and caregiver responses, Hypothesis 2a will be tested by an adolescent group by caregiver group by time interaction, or by an adolescent by caregiver interaction if the four adolescent by caregiver group trends are parallel.

Aim 3 (Secondary Outcome). Working hypothesis 3a (change in neurocognitive and academic factors) will be tested using the same mixed effects models as outlined above in aims 1 and 2. Working hypothesis 3b (mediation), whether improvement in neurocognitive variables (e.g. impulse control) or academic WRAT scores partly account for the treatment effect on child behavior will be assessed using mediation analyses. Based on the prior study (Raine et al, 2015), effects of supplementation should emerge by the 12-month time point. Analyses will test whether changes in risk factors between baseline and the 6 month point mediate the 12-

month treatment effect. These analyses will be conducted using the PROCESS SPSS macro (Hayes, 2012), which will also be used to assess moderated mediation (e.g. neurocognitive measures mediate outcomes more strongly in younger adolescents). To test significance of the indirect effects (i.e. mediation), bias-corrected confidence intervals for the indirect effects will be generated using 10,000 bootstrap samples. To assess extent of mediation, the reduction in variance explained in treatment outcome by the intervention after controlling for improved parental behavior (the mediator) will be calculated in a two-step regression. Equivalent analyses will be performed for the other neurocognitive variables.

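### No adverse-event question is scheduled at months 12 and 18, although the plan expects its effects to emerge by month 12

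*Combined protocol and SAP*

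**What the plan says.** **Harms.** Under Secondary Outcome Measures, the paragraph on treatment belief and demographics adds "together with an adverse events questionnaire at the end of treatment". No other adverse-event collection, and no adverse-event analysis, is described. The fortnightly calls during supplementation (Adherence to protocol and blood assays) are for reminders and drink counts, with no stated question about harm.

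**Timing of treatment and visits.** Omega-3 Intervention states: "As in the pilot study, treatment duration will be six months". Design Overview places the follow-up assessments at "6 months (end of supplementation), 12 months (6 months post-treatment), and 18 months (12 months post-treatment").

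**Timing of the expected effect.** Statistical Methods, Aims 1 and 2, treats time as a discrete factor because in the pilot "the omega-3 adolescent groups are similar at baseline and 6 months, and separate at 12 months". Aim 3 says that "effects of supplementation should emerge by the 12-month time point" and builds the mediation analysis on the 12-month treatment effect.

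**What else is measured late.** Externalizing scores are analysed at months 0, 6, 12 and 18 in both generations. The same family of instruments carries symptom scales: "the Internalizing scale includes Anxious/Depressed, Withdrawn, and Somatic Complaints" (Primary Outcome Measures).

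**The concern.** Closing harm collection at the end of dosing is easiest to defend when effects are expected during dosing. This plan expects its main effect to become visible as late as six months after the last drink, and it keeps participants under assessment for a year after treatment to capture it. A plan built on that premise has little ground for assuming that every unwanted effect will have appeared by month 6.

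A second gap does not depend on delayed effects. An event still unresolved at month 6 has no described point at which its outcome is recorded, although the same adolescent and caregiver are due back twice.

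At stake is how complete the safety account will be when the 12- and 18-month results are reported. Any statement about tolerability would rest on one retrospective questionnaire taken before the period in which the main effect is looked for. No primary or secondary efficacy analysis is affected.

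**Working it through.** **Step 1: the plan's own timing and numbers.** Time since treatment is visit month minus 6: 12 − 6 = 6 and 18 − 6 = 12, which agrees with Design Overview. Total N is 4 cells × (100 adolescents + 100 caregivers) = 800, which agrees with the Participants section. Each generation has 2 × 100 = 200 people on omega-3 and 200 on placebo.

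**Step 2: what is asked, and when.**

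| Month | Externalizing score | Adverse-event question |
|---|---|---|
| 0 | yes | no |
| 6 (end of supplementation) | yes | yes |
| 12 (pilot adolescent groups separated) | yes | no |
| 18 | yes | no |

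The questionnaire's recall period is not stated. If it reaches back over all of supplementation, the adverse-event window is at most 6 of 18 months (33%), leaving (18 − 6)/18 = 67% with no adverse-event question. This describes the schedule; it is not an estimate of harm missed.

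**Step 3: what would still be recorded after month 6.** Externalizing scores at months 12 and 18 can move in either direction, and the group-by-time tests are not restricted to benefit, so behavioral worsening would be visible. Emotional and some somatic symptoms would probably be visible too, if the whole instrument is repeated as the general visit schedule implies; the statistical section confirms late timing explicitly only for externalizing. What remains is other medical events, together with the onset, seriousness and resolution of any event, which symptom scores do not capture.

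**Step 4: what repeating the questionnaire would yield.** The documents give no adverse-event rates, so the risks below are assumptions. The two sample sizes are all 200 omega-3 recipients in one generation, and 200 × (1 − 0.08) = 184, using the pilot's one-year attrition of 8%. The plan itself says attrition may be slightly higher over the longer follow-up.

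Chance of recording at least one event = 1 − (1 − p)^n:

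| Assumed post-treatment risk p | n = 200 | n = 184 |
|---|---|---|
| 0.5% | 63% | 60% |
| 1% | 87% | 84% |
| 2% | 98% | 98% |
| 5% | >99.9% | >99.9% |

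With no events, the 95% upper limit on the risk is 1 − 0.05^(1/n): 1.5% for n = 200 and 1.6% for n = 184.

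**Step 5: what it would not yield.** Taking 184 per group in one generation and a two-sided 5% normal-approximation test, power is about 35% for 2% versus 5%, 44% for 5% versus 10%, and 90% for 5% versus 15% (assumed rates again). Late harms data would support description and an upper bound, and a formal comparison only for large differences. Hence the descriptive tabulation recommended under the fix.

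**The case against.** The strongest reply is that asking about harms at the end of exposure is a coherent choice, that no passage contradicts it, and that late harm is an analogy. Much of this stands. The pilot pattern concerns behavior in adolescents; it says nothing about caregivers or adverse events. It makes late harm plausible and no more.

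Several stronger readings are tempting, and the documents do not support them:

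- **That the plan treats fish oil as active for six months after use.** A reader might infer this from the exclusion for "use of fish oil supplementation in the past six months". No reason is given for that criterion, and it could equally serve to secure a supplement-free baseline. No carry-over period, or share of one, can be derived from it.
- **That late blood sampling shows the plan regards participants as still exposed.** The plan takes "finger-prick blood taken from both caregiver and adolescent at all four time-points", but the stated purpose is adherence.
- **That the plan says biological effects appear only after supplementation.** It says effects should emerge by month 12, and its mediation analysis looks for risk-factor changes between baseline and month 6. That is change during supplementation followed by later behavior.
- **That late harm would be invisible, or the benefit-harm comparison one-sided by design.** Step 3 shows that behavioral harm would be recorded, and emotional and some somatic harm probably would be.

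It is also fair to say that the text is incomplete. It opens at the design section and refers to preliminary data and hypotheses not included here. Spontaneous reporting, or follow-up of open events, may be set out elsewhere.

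What these points do not answer is the narrower gap. Symptom scores analysed as outcomes do not identify events or say whether they resolved, and the described plan asks about events only once. More frequent questions during months 0 to 6 would not close it.

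**Conclusion.** The point holds in a limited form. As described, adverse events are asked about once, at month 6, and the remaining 12 of 18 months have no adverse-event question, although the plan expects its effect to emerge by month 12 and already has visits at months 12 and 18. Delayed events, and events unresolved at month 6, that lie outside the behavioral and symptom scales would not be systematically recorded.

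This rests on three conditions: that the visible text describes all scheduled adverse-event collection; that the questionnaire looks back no earlier than the start of treatment; and that late harm is worth checking for because the plan's own effect is late. The documents supply no evidence that such harm occurs and no rate from which to estimate it. The point is an inexpensive improvement to the safety record and does not undermine the efficacy analyses.

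**What to change.** In the Secondary Outcome Measures paragraph that introduces the adverse-events questionnaire, state that the same questionnaire is given to both adolescent and caregiver again at the 12- and 18-month visits, asking about (a) events since the last visit and (b) the outcome of any event open at month 6. State the recall period at each administration.

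In Statistical Methods, add that adverse events will be tabulated descriptively, separately for adolescents and caregivers, by the recipient's own randomized drink and by period (months 0–6, 6–12, 12–18), without formal testing of each cell. If follow-up of open events or later reporting is already set out in another document, a cross-reference would suffice for that part.

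The cost is a sentence or two of protocol text, a few minutes at two visits already scheduled, and a little data entry. Some background events unrelated to the drink will be recorded; the randomized placebo groups show how common those are. No visit or procedure is added, and nothing in the intervention or its management changes.

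### The only adverse-event collection described is one questionnaire at month 6, although families are already phoned every two weeks: early transient events are likely to be under-reported, and early leavers have no stated route to a record

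*Combined protocol and SAP*

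**What the plan says.** Under Secondary Outcome Measures, the paragraph on treatment belief and demographics plans baseline demographics "together with an adverse events questionnaire at the end of treatment". Adverse events are not mentioned anywhere else in the document.

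Under Treatment duration and administration, "treatment duration will be six months".

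The section on adherence and blood assays provides two kinds of contact while participants are taking the drink. First, "participants will be called every two weeks to remind them to use supplements, and to assess frequency of drink consumption by caregiver and adolescent". Second, a blood sample is added at 3 months. Neither contact is said to ask about adverse events.

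The section on participants and attrition plans 400 pairs, "with 100 children and 100 adults in each of four cells". It gives the pilot's attrition as 8% at one year and expects slightly more over the longer follow-up here, without a figure. Intention-to-treat is the rule for all analyses. Statistical Methods describes no summary of adverse events.

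**The concern.** A single form at the end of treatment has two weaknesses.

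- **Recall.** A mild complaint in the first weeks has to be remembered, dated and attributed to the right family member up to six months later. The plan asks about drink consumption over two-week periods but leaves side effects to a recall period of up to six months.
- **Coverage.** A form tied to month 6 does not, as described, reach someone who has left by then. Intention-to-treat does not repair this, because it governs who is analysed and cannot supply events that nobody asked about.

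A lesser point is that parental belief about allocation is recorded at the same time as the questionnaire. Side effects recalled at that moment may be coloured by that belief more than reports made during treatment would be.

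What is at stake is the trial's description of tolerability. By design 200 adolescents and 200 caregivers receive omega-3 (two of the four cells for each, at 100 per cell). No efficacy estimate depends on this point.

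**Working it through.** The plan states no adverse-event rate, recall period or early drop-out figure, so there is nothing of its own to reproduce beyond the sample size: 4 cells × (100 children + 100 adults) = 800, which agrees with the stated total.

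**Recall period.** Six months is about 26 weeks. Calls every two weeks give 26 / 2 = 13 calls per family if they run throughout treatment. Asking at each call would replace one inquiry with about 13, and the longest gap would fall from about 26 weeks to about 2.

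**What month-6 recall might capture.** Assume that transient events start uniformly over 26 weeks and that a respondent reliably recalls only the last *w* weeks. The share captured is *w* / 26. Both assumptions are illustrative and neither comes from the documents.

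| *w* (weeks) | Share captured |
|---|---|
| 2 | 8% |
| 4 | 15% |
| 8 | 31% |
| 13 | 50% |
| 26 | 100% |

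If onset is concentrated early in treatment, the share captured is lower for any *w* short of 26.

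**People who leave before month 6.** The only figure available is the pilot's 8% at one year. The share lost before month 6 is not given, so a range of 2% to 8% is assumed:

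- 400 × 0.02 = 8 pairs; if both members leave together, 16 people.
- 400 × 0.08 = 32 pairs; if both members leave together, 64 people, or an average of 64 / 4 = 16 of the 200 people in each cell.

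If only one member of each such pair leaves, the figures are 8 to 32 people. The 8% end would be an upper bound only if attrition matched the pilot, since only losses before month 6 count. The plan expects somewhat more attrition overall, so 8% is not a strict ceiling.

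**Cost of asking at the calls.** 400 pairs × 13 = 5,200 calls. At an assumed one extra minute per pair, 5,200 / 60 ≈ 87 hours over the trial. At one minute per person, 10,400 / 60 ≈ 173 hours.

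**The case against.** The strongest reply is that the point rests on silence. The text begins at the methods and refers to a preliminary-data section that is not included. Consent pages, which may tell families how to report problems, are not part of what was reviewed. A separate safety procedure may exist. This stands, and it limits the claim to what these documents describe.

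Several stronger readings are tempting, and the documents do not support them:

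- *A reader might infer that early and transient events are lost.* A month-6 form recovers some of them by recall, and nothing says that leavers will not be contacted. The text supports likely under-reporting.
- *A reader might infer that problems would come to notice only after exposure has ended.* Staff speak to families every two weeks about drink use and see them at 3 months, so intolerance could surface then. What is missing is a stated, systematic record.
- *A reader might infer that early leavers mostly left because of side effects, so that the omega-3 arms are under-counted.* The documents give no reasons for drop-out, no attrition by arm and no event rates.
- *A reader might take 64 people as the size of the gap.* That figure needs the one-year pilot rate to apply before month 6 and both members to leave together. Stopping the drink is also not the same as leaving the study: someone who stops but attends at month 6 can still complete the form, and the plan offers incentives for completion.

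There is also a fair objection to the remedy. Repeated questions about side effects could prompt guesses about allocation among caregivers and adolescents, who supply ratings for the primary outcome. The risk is real but small, and identical questions would put it on all arms alike.

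**Conclusion.** The point holds as an inexpensive improvement to data collection. It is not an error or an internal contradiction, and it does not touch the efficacy analysis. As described, the plan relies on recall of up to about 26 weeks and gives no route to an adverse-event record for those who leave before month 6. Under the stated assumptions the second gap covers 8 to 32 pairs (16 to 64 people). The recall weakness applies to all 800 participants whatever the attrition. The direction and size of any difference between arms are unknown. If a fuller safety procedure exists elsewhere, a cross-reference to it would settle most of the point.

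**What to change.** 1. Add one brief, neutrally worded adverse-event question (what, when, caregiver or adolescent) to each two-weekly call and to the 3-month blood contact. Use identical wording in all arms.
2. Give the existing questionnaire to anyone who stops the drink or leaves the study early, at that time. Keep the month-6 form for everyone else.
3. State in Statistical Methods that events will be tabulated by the person's own allocation, and also by the four cells, for all randomised participants. This keeps to the plan's intention-to-treat rule. Show those who took any drink as a supplementary set.

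The cost is about 5,200 slightly longer calls, roughly 87 to 173 hours over the trial at the assumed one minute per pair or per person, before any time spent on recording and follow-up. No extra visits are needed. The planned end-of-treatment belief question gives a check on allocation guessing among caregivers. No equivalent question is described for adolescents.

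### The compliance bonus is paid on blood omega-3, which only the treatment drink supplies, so under any threshold common to both arms pay follows allocation rather than placebo compliance and partly signals the arm

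*Combined protocol and SAP*

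**What the plan says.** All references are to the combined protocol and SAP.

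- **Adherence to protocol and blood assays.** Adherence is measured in blood: "this will be assessed by assays of omega-3 from finger-prick blood taken from both caregiver and adolescent at all four time-points". A further sample is taken at 3 months. Participants are phoned every two weeks with a reminder and asked how many drinks were taken. The bonus has a stated purpose, "To further facilitate compliance", and its rule reads as follows: "participants will be given a bonus payment if their % blood omega-3 levels have risen higher than the bottom quartile of the population". The section does not define the population, say whether a rise from the person's own baseline is needed, or say when the bonus is paid and by whom. Masking of results or payments is not described.
- **Omega-3 Intervention.** Both drinks share a base of fruit juice with vitamin D and antioxidants. "For the treatment condition only, 1660 mg of omega-3" is added. The drinks are matched in size, appearance and flavor.
- **Design Overview.** The trial is described as a "stratified, double-blind, placebo-controlled, factorial, randomized controlled trial".
- **Primary Outcome Measures.** The adolescent completes the YSR. The caregiver completes the CBCL on the child, the ASR on themselves and the ABCL on the spouse. Teachers also rate the child.
- **Secondary Outcome Measures.** Parents are asked once, at the end of treatment, whether they believe allocation was to omega-3.

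**The concern.** The bonus is meant to reward taking the drink, but its trigger is a quantity that only one of the two drinks is designed to change. Two consequences follow if the treatment drink raises blood omega-3, which using the assay as an adherence measure presumes.

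First, the chance of being paid differs by arm, and a placebo participant who never misses a drink has no better chance than one who takes none.

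Second, being paid or not carries information about allocation. Matching the drinks cannot hide this, because the information comes through the payment. The people eligible for the bonus are also those who rate most of the primary outcome. Blood is drawn at 3 and 6 months, and the Aim 3 analysis text expects effects to emerge by 12 months, so a result or payment after either sample could reach raters before the ratings that matter most.

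**Working it through.** **No stated figure to reproduce.** The plan gives no bonus rate, blood omega-3 distribution or expected rise. The core of the point rests on setting two sections side by side.

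1. The trigger is % blood omega-3 (adherence section).
2. Omega-3 is added to the treatment drink only (intervention section).
3. So taking the placebo drink changes the chance of payment by zero, while taking the treatment drink raises it if blood levels rise.
4. With one threshold for both arms, a positive shift in one arm gives unequal payment. With no shift, payment is equal and there is no signal.

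**Illustration of size.** Everything here except the arm sizes is assumed. Each drink goes to 2 cells × 100 = 200 adolescents and 200 caregivers, so 400 people per arm. Levels are in SD units: baseline X0 ~ N(0,1); follow-up X1 ~ N(s,1), with s = 0 on placebo and s = 1 on omega-3; correlation of X0 and X1 is r = 0.7. The population quartile is c = −0.6745. The change X1 − X0 is N(s, 2(1−r)), with SD √0.6 = 0.775.

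Five readings of the rule, each with one threshold for both arms:

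- A: level above the population quartile, P(X1 > c).
- B: as A, and above own baseline, P(X1 > c and X1 > X0).
- C: change above the bottom quartile of change in both arms pooled.
- D: crossing from at or below the quartile to above it, P(X0 ≤ c and X1 > c).
- E: change above the bottom quartile of omega-3-arm changes, 1 − 0.6745 × 0.775 = 0.478.

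With p0 and p1 the payment probabilities on placebo and omega-3, and equal arms:

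- correct guesses of arm = 0.5 × (p1 + 1 − p0)
- P(placebo given unpaid) = (1 − p0) / [(1 − p0) + (1 − p1)]
- P(omega-3 given paid) = p1 / (p0 + p1)

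| Reading | p0 | p1 | Gap | Correct guesses | P(placebo given unpaid) | P(omega-3 given paid) |
|---|---|---|---|---|---|---|
| A | 0.750 | 0.953 | 0.203 | 60% | 84% | 56% |
| B | 0.425 | 0.869 | 0.444 | 72% | 81% | 67% |
| C | 0.571 | 0.929 | 0.358 | 68% | 86% | 62% |
| D | 0.100 | 0.210 | 0.110 | 56% | 53% | 68% |
| E | 0.269 | 0.750 | 0.481 | 74% | 75% | 74% |

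Worked example, reading A: correct guesses = 0.5 × (0.953 + 1 − 0.750) = 0.60. Unpaid: 400 × 0.250 = 100 on placebo against 400 × 0.047 ≈ 19 on omega-3.

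**Sensitivity.** Over s from 0.5 to 2 and r from 0.5 to 0.9, correct guesses are 56–62% (A), 60–80% (B), 58–75% (C), 53–59% (D) and 59–87% (E), against 50% by chance. The payment gap runs from 5 points (D) to 75 points (E). The top of both ranges comes from E alone; without it the maxima are about 80% and 59 points. Whether paid or unpaid status is the stronger clue depends on the reading and, for E, on the assumed values: at s = 1 and r = 0.9, E gives 79% for unpaid against 93% for paid.

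**The case against.** Four objections have force.

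**Motivation is not payoff.** A reader might infer that the incentive works in the omega-3 arm only. The documents do not support that. An incentive acts through what people expect, and with matched drinks a blinded placebo participant may hope for the bonus as much as anyone, at least until results or payments are known. The zero for placebo is the effect of drinking on pay, not on compliance.

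**Unequal pay is not certain under every conceivable rule.** The population is undefined. If quartiles were taken within each arm by someone holding the codes, about 75% would be paid in each. Nothing in the text suggests this, and pay would still be unrelated to placebo drinking, but the claim of unequal pay must be limited to a common threshold.

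**Unblinding and bias are not shown.** A reader might infer that the bonus breaks the blind. That requires participants to know the criterion, learn their result before later ratings, and rate differently as a result. Participant information about payments may lie in consent pages that are not in the available text. There is also some separation: the document has "with microwave irradiation assays conducted by team member" at another institution, while "The study will take place in interview rooms at the project headquarters in Quatre Bornes". Even so, someone must receive results or a pay list, and the plan does not say who. The belief item could detect a leak from the 3-month sample among parents. It misses adolescents and anything learned after 6 months, and it prevents nothing. Teacher ratings are less exposed.

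**Outside supplements.** It is tempting to add that the bonus rewards fish oil from other sources, given the exclusion for "use of fish oil supplementation in the past six months". That is an entry criterion, and nothing shows that the bonus would prompt use during the trial, so no weight is placed on it.

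**Conclusion.** The point holds, within limits. As written, the rule ties a compliance payment to a marker that placebo cannot be expected to move. Provided that the treatment drink raises blood omega-3 and the threshold is common to both arms, pay is unequal by arm, some fully compliant placebo participants are refused, and payment status partly signals allocation. This is a flaw in a stated rule, not merely missing detail.

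The size cannot be fixed from the documents. On the assumed values, payment is 10–75% on placebo against 21–95% on omega-3, and arm is guessed correctly 56–74% of the time (53–87% over the wider range). Harm to the 12- and 18-month ratings remains a possibility that the plan leaves open, not a demonstrated bias. Label: cheap improvement.

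**What to change.** In the adherence section, replace the blood criterion with an arm-neutral one that uses activities already planned: completing the finger-prick samples and the two-weekly calls. Keep blood omega-3 as the adherence measure, but masked: withhold results from participants, callers and assessors until database lock.

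If a blood-based bonus is kept, define the population and the rule, and have a party with no participant contact pay it after the 18-month ratings. That limits the leak but leaves pay unequal.

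The cost is a short change to protocol and consent wording, with no new data collection. The real downside is that an arm-neutral bonus rewards participation rather than drinking, so the direct incentive to drink is weaker in both arms. It also partly overlaps the completion incentives in the section on participants and attrition.
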